3	Sample Banking		Sample banking for future study	Frozen tumor tissue (when available)	1) Available archival tissue  2) Pulmonary Metastases resected from staged resection at enrollment and then after one cycle of protocol therapy (cohort B4 only)  3) Clinical biopsies obtained during therapy or at disease progression	Optional	EET Biobank

Priority	Biomarker Name	Assay (CLIA: Y/N)	Use in the Trial (Integral, Integrated, or Exploratory) AND Purpose	Specimens Tested	Collection Time Points	Mandatory or Optional	Assay Laboratory and Lab PI
4	CyTOF for immune subsets	Mass Cytomet ry CLIA: N	Exploratory  To determine changes in the peripheral immune subsets as a result of treatment with anti-CD47 / anti-GD2	marrow in	1) Baseline 2) Disease restaging (cycle 2, 4, 8, 12) 3) End of therapy	1) Nandatory (fresh or viably frozen) 2) Nandatory 3) Coptional	.edu
5	Sample Banking		Sample banking for future study	Mononucle arcells and plasma from bone marrow in Sodium Heparin and EDTA tubes (Bilateral)	Baseline if available  Disease restaging (cycle 2, 4, 8, 12)  End of therapy	Optional	EET Biobank
Blood-b	ased Biomark	ers		•			
1	Magrolimab PK	ELISA CLIA: N No Review Require d	Integrated Assess the drug concentrations achieved during this first in child trial	Serum from Red top tube	Safety lead-in D1, 8, 15 Cycle 1, D1, 8, 15, ARM B only: D22 Cycle 2, D1 Cycle 3, D1 Cycle 5, D1 Cycle 7, D1 Cycle 9, D1 Cycle 11, D1 End of therapy (all samples drawn prior to magrolimab infusion)	M (safety cohort and first three patients on any expansion cohorts)	PPD

Version Date: 02/02/2024

Priority	Biomarker Name	Assay (CLIA: Y/N)	Use in the Trial (Integral, Integrated, or Exploratory) AND Purpose	Specimens Tested	Collection Time Points	Mandatory or Optional	Assay Laboratory and Lab PI
2	Magrolimab anti-drug antibody (ADA) Testing	ECLIA CLIA: N No Review Require d	Integrated Assess for immune responses against magrolimab	Serum from Red top tube	Safety lead-in D1  Cycle 1, D1  Cycle 2, D1  Cycle 3, D1  Cycle 5, D1  Cycle 7, D1  Cycle 9, D1  Cycle 11, D1  End of therapy  (all samples drawn prior to magrolimab infusion)	M (safety cohort and first three patients on any expansion cohorts)	PPD

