Level -1	20 mg/kg IV		17.5 mg/m  IV
Level 1	30 mg/kg IV		17.5 mg/m  IV

The dose level of Hu5F9-G4 (magrolimab) that is deemed safe during both the 'Single agent Safety Lead-In' and Cycle 1 in the dose finding cohort (Arm A) will be used to evaluate safety in the Arm B schedule. The first three (3) patients enrolled to Arm B will be evaluated for DLT, and three weeks (21 days) must elapse after completion of Cycle 1 in the final patient to allow for safety assessment before treating additional patients in Arm B to confirm the recommended phase 2 dose (RP2D) (Arm B) (see Section 6.2.1.2). These three patients will be allocated and analyzed in their respective cohorts for efficacy analysis.

If protocol therapy is delayed (due to re-scheduling for administrative reasons or temporary suspension due to toxicity), disease evaluations and correlative exploratory biology studies will follow the originally scheduled calendar dates and should *not* be adjusted for the dose delay. The results of these evaluations and assays while on treatment should reflect the effect of the former dose(s), not the current/prospective clinical status at the time of drug administration. All clinical assessments and laboratory tests (and their respective windows) will adjust with the dose delay to reflect the patient's clinical

status at the time of drug administration.

The Study Calendars in Section 11 outline the timing of procedures and visits for Arm A and Arm B.

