# 9.5 Analysis of Secondary Endpoints

**9.5.1** Determine the pharmacokinetics (PK) of Hu5F9-G4 (magrolimab) in children and young adults.

The endpoint for PK analysis is to assess the drug concentrations achieved during this first in child trial. Samples will be collected in the Safety Lead-In cohort and the first 3 patients on any expansion cohorts on the following schedule:

- Safety Lead-In: Day 1, Day 8, Day 15
- Cycle 1: Day 1, Day 8, Day 15
- Cycle 2, 3, 5, 7, 9, 11: Day 1
- End of Therapy

These samples will be a mandatory in the Safety Lead-In cohort and in the first three patients on any expansion cohorts (B1, B2, B3 and B4).

The PK Analysis Set will be used for summaries of PK concentration of magnolimab versus time. Serum concentrations will be listed and summarized for magnolimab using descriptive statistics by sampling timepoint and cohort. Graphical plots of individual serum concentration versus time and mean concentration versus time by cohort will be generated. The samples will be tested and analyzed by PPD.

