  - Patients removed from protocol therapy for unacceptable AE(s) will be followed until resolution or stabilization of the AE. In addition, these patients will complete the EOT, Safety, and Follow-up Visits according to protocol.
- All blood draws for correlative exploratory biology studies will be performed according to the schedule outlined in Table 3, Specimen Collection Schedule; and Section 5. All blood draws for correlative exploratory biology studies must be performed prior to dosing. If treatment is delayed, blood draws for correlative exploratory biology studies will follow the originally scheduled calendar dates and should not be adjusted for the dose delay.
- Archival slides will be requested from all patients. If available, clinical biopsies or surgical samples obtained during treatment or at disease progression will be requested.
-  After Cycle 2, Hu5F9-G4 (magrolimab) will be administered ONLY on Day 1 of week 1 and 3 only (week 2 will be a week of rest).
- Bone marrow aspirations will be conducted in all patients with neuroblastoma/ganglioneuroblastoma (as per INRC). Week 1, Day 1 collection is mandatory, *except* if viably frozen bone marrow aspirate collected within 4 weeks (28 days) of the Priming dose (Week 1, Day 1) is available and can be provided to the EET Biobank. Bone marrow aspirates are required at all disease assessment timepoints (end of Cycle 2, 4, 8 and 12). Bone marrow aspirate at End of Therapy is optional.
- Within 24 hours prior to the Priming dose (Week 1) of Hu5F9-G4, hemoglobin must be ≥ 9.5 g/dL. Within 24 hours prior to the first full dose (Week 2) of Hu5F9-G4, hemoglobin must be ≥ 9.0 g/dL (see Section 6.2.1.3). Hemoglobin must be checked 3 to 6 hours after the initiation of the first and second doses of Hu5F9-G4 (magrolimab).

THIS PROTOCOL IS FOR RESEARCH PURPOSES ONLY, SEE PAGE 1 FOR USAGE POLICY

Baseline/screening evaluations are to be conducted within 4 weeks (28 days) prior to start of protocol therapy. Scans must be done < 4 weeks (28 days) prior to the start of protocol therapy. In the event that the patient's condition is deteriorating, laboratory evaluations should be repeated within 48 hours prior to initiation of the next cycle of therapy.

Treatment Cycles/Visits	Screening	Treatment								Follow Up		
		Priming Cycle 1				Cycle 2 and subsequent cycles			End of	G 6 /	E II II 17	

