# APPENDIX N: HUMAN ANTI-CHIMERA ANTIBODIES (HACA) TESTING WORKSHEET FOR ARM A

COG Pt ID #				
	ient names on this form or	r on samples.		
Patient Weight:	kg			
Hu5F9-G4 (Magrolii	mab) Dose:1		l Daily Dose:	mg IV infusion
Dinutuximab Dose:	1	ng/kg Tota	l Daily Dose:	mg IV infusion
-	be collected in red top t	s drawn	).	
Blood Sample No.	Time Point	Scheduled Collection Time	Actual Date Sample Collected	Actual Time Sample Collected (24-hr clock)
1	Cycle 1, Day 1	Prior to dinutuximab infusion	/ /	(24-11 Clock)
2	Cycle 1, Day 5	Immediately after dinutuximab infusion	//	_ _ : _
Blood Sample No.	Time Point	Scheduled Collection Time	Actual Date Sample Collected	Actual Time Sample Collected (24-hr clock)
3	Cycle 2, Day 1	Prior to dinutuximab infusion	/ /	:
4	Cycle 2, Day 5	Immediately after dinutuximab infusion	//	_ . : _
		mosion		
Blood Sample No.	Time Point	Scheduled Collection Time	Actual Date Sample Collected	Actual Time Sample Collected (24-hr clock)
5	Cycle 4, Day 1	Prior to dinutuximab infusion	//	
6	Cycle 4, Day 5	Immediately after dinutuximab infusion	//	_ _ :
			1	
Blood Sample No.	Time Point	Scheduled Collection Time	Actual Date Sample Collected	Actual Time Sample Collected (24-hr clock)
7	End of Therapy		/ /	
One copy of this HA	.CA Form should be up	ploaded into RAVE. A second copy should es for packaging and shipping samples.	d be sent with the sar	 
If this form will be u	sed as a source docume	ent, the site personnel who collected the sa	imples must sign and	date this form below:
Signature: (site personnel respo	nsible for collection of	samples)	Date:_	

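### After a dose delay, correlative blood draws stay on their original dates: the post-dinutuximab HACA sample can then precede the infusions it should follow, and later pre-dose draws lose their planned interval to dose

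*Combined protocol and SAP*

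**What the plan says.** Section 6.1.1.2 states that, when therapy is delayed for administrative reasons or toxicity, "disease evaluations and correlative exploratory biology studies will follow the originally scheduled calendar dates". Its stated purpose is that on-treatment results should show the effect of doses already given. Footnote 18 of the Arm A calendar, repeated for Arm B, applies the same rule to blood draws: "blood draws for correlative exploratory biology studies will follow the originally scheduled calendar dates and should not be adjusted for the dose delay". It also says that all of these draws "must be performed prior to dosing". Clinical laboratory tests, by contrast, move with the dose (Section 6.1.1.2 and footnote 13).

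The draws themselves are defined by a dose:

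- **PK and ADA (Table 2):** "all samples drawn prior to magrolimab infusion".
- **Cytokines and CyTOF (Table 2 and worksheets):** weekly before magrolimab in the lead-in and Cycles 1 and 2, then on Day 1 of later cycles.
- **HACA (Tables 2 and 3, Appendices N and O):** one draw before dinutuximab and one on Day 5 (Arm B Cycle 1: Day 12). The worksheets time the second as "Immediately after dinutuximab infusion".

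Section 9.5.1 summarises magrolimab concentrations "using descriptive statistics by sampling timepoint and cohort". In the expansion cohorts, Section 6.4 says that doses are delayed rather than skipped, and it stops protocol therapy for delays beyond 14 days, with exceptions.

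**The concern.** Once the dose moves and the draw does not, a sample can carry a label that no longer describes it. For HACA, a sample labelled post-infusion may be taken before any infusion of that cycle, and a post-infusion sample that was never taken cannot be recovered afterwards. For the other assays, samples under one label come from different times after dose in delayed and undelayed patients, and a summary by label mixes them.

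At stake are secondary objective 1.2.1 (PK) and exploratory objective 1.3.1 (HACA, ADA, cytokines, immune subsets). PK sampling is mandatory only in the lead-in cohort and the first three patients of each expansion cohort. If only those three contribute, one displaced patient is a third of a cohort mean.

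**Working it through.** **Which assays the rule reaches.** PK and ADA are described in 5.1.2 and 5.1.3, under the heading for exploratory and ancillary correlative studies. The calendar has one blood-sample row. It carries footnote 18, which points to Table 3 and Section 5. On that reading the rule covers PK, ADA, HACA, Luminex and CyTOF. Table 2 labels PK and ADA as integrated rather than exploratory, so the coverage is inferred and should be stated.

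**Inputs.** Arm B calendar: priming on study day 1; Cycle 1 magrolimab on days 8, 15 and 22; Cycle 2 Day 1 on day 29; 21-day cycles after that. Magrolimab is given on Days 1, 8 and 15 of Cycle 2 and on Days 1 and 15 from Cycle 3. Dinutuximab is given on Days 2 to 5. Cycle 2 Day 1 and all later doses are delayed by d days (0 to 14), and draws stay on their original dates. A draw due on a magrolimab day is taken before that dose. The Day 5 HACA draw is taken after any dinutuximab infusion given that day.

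**HACA.** Infusions move from Days 2–5 to Days 2+d to 5+d, and the draw stays on Day 5. Infusions given before the draw = max(0, 4 − d).

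**Pre-dose draws.** The Cycle 2 Day 1 draw is always 7 days after the Cycle 1 Day 15 dose and still before the delayed dose, so it keeps its planned interval. Later draws do not. The original Cycle 5 Day 1 date is actual Cycle 4 Day 22 − d. For d = 1 to 6 the last dose is Day 15, so the interval is 7 − d. For d = 7 to 14 the last dose is Day 1, so the interval is 21 − d.

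| Delay d (days) | Infusions before the Day 5 HACA draw (Cycles 2 and 4) | Cycle 3 Day 1 draw: days since magrolimab | Cycle 5 Day 1 draw: days since magrolimab |
|---|---|---|---|
| 0 (plan) | 4 of 4 | 7 | 7 |
| 1 | 3 of 4 | 6 | 6 |
| 2 | 2 of 4 | 5 | 5 |
| 3 | 1 of 4 | 4 | 4 |
| 4 | 0 of 4 | 3 | 3 |
| 6 | 0 of 4 | 1 | 1 |
| 7 | 0 of 4 | 7 | 14 |
| 10 | 0 of 4 | 4 | 11 |
| 14 | 0 of 4 | 7 | 7 |

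A 7-day interval in the last rows does not restore the plan. At d = 7 the Cycle 3 Day 1 draw precedes the third Cycle 2 dose, and at d = 14 it precedes the second.

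A delay starting at Cycle 4 shows the HACA problem directly. With d = 7, the Cycle 4 Day 5 sample falls 21 days after the last dinutuximab infusion (Cycle 3 Day 5) and 4 days before the next, so the before/after pair contains no infusion.

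**Size for PK.** Section 2.1.6 gives a terminal half-life of about 2 weeks at 10 mg/kg weekly or more. Assume one-compartment decay, steady state, equal doses on Days 1 and 15 of 21-day cycles, and k = ln 2/14.

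- Planned draw, 7 days after dose: (e^−7k + e^−21k)/(1 − e^−21k) = (0.707 + 0.354)/0.646 = 1.641.
- Cycle 5 Day 1 draw at d = 7, 14 days after dose: (e^−14k + e^−21k)/(1 − e^−21k) = (0.500 + 0.354)/0.646 = 1.320.
- Ratio: 1.320/1.641 = 0.805, about 20% lower. For assumed half-lives of 10 and 21 days the ratio is 0.721 and 0.873.

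The shift can also go upward. At d = 6 the draw comes 1 day after dose instead of 7, and the same model gives 2^(6/14) = 1.35 times the planned level.

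**The case against.** The rule is deliberate. It does what it intends at the delayed dose, where the sample keeps its 7-day interval and shows the effect of earlier dosing. Moving that draw would put it 7 + d days after the previous dose. At d = 7 and a 14-day half-life, that reading is lower by the factor e^−7k = 0.707, or 29% (21% to 38% for half-lives of 21 to 10 days). This is more than the 20% above, although it affects one draw. So moving draws does not by itself make labels comparable. This stands, and it is why the PK analysis must also use actual time since dose.

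A reader might infer that samples of all five assay groups cease to bracket a dose. The documents do not support that: only HACA has a post-infusion draw. A displaced PK sample can also remain pre-dose, as at d = 7, where the Cycle 5 Day 1 draw falls on actual Cycle 4 Day 15.

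A reader might also infer that the PK data are spoiled. The PK and ADA worksheets record sample time, dose date and infusion start and stop, so time since dose can be recovered, and Section 9.5.1 also plans plots of individual concentrations against time. What is missing is a plan to use actual times in the summaries.

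Nor can the misplacement be called simply toxicity-driven, since Section 6.1.1.2 names administrative rescheduling too.

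Finally, footnote 18 sends sites to Table 3. A site following Table 3 or Appendices N and O would draw HACA after the actual infusion. The texts therefore conflict; they do not show that samples will be misplaced. But a site following the footnote literally loses the sample.

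**Conclusion.** The point holds in a limited form. For HACA the documents contradict themselves without any delay, and under the calendar rule a delay of 4 to 14 days leaves the post-infusion sample with none of that cycle's infusions before it. This follows from day counting alone.

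For PK, ADA, cytokines and CyTOF, the draw at the delayed dose is sound. Later draws vary from 1 to 14 days after dose in the cases worked, against 7 planned. The PK effect of about 20% rests on an assumed steady state and on the half-life from the first-in-human study; it illustrates one 7-day delay. Persistence of the misalignment rests on later doses shifting with the delayed one, which Section 6.4 states for the expansion cohorts.

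A reader might infer that dose selection or the cohort response decisions are at risk. They are not: those rest on DLTs and on disease evaluations, for which fixed dates are reasonable because a delay then does not postpone detection of progression. Section 9.5 contains no analysis of HACA, ADA, cytokines or immune subsets, so the consequence for objective 1.3.1 is a loss of interpretable samples rather than an error in a planned test.

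**What to change.** In Section 6.1.1.2 and footnote 18 of both calendars:

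- keep the fixed-calendar rule for disease evaluations;
- tie the pre- and post-dinutuximab HACA draws to the actual infusion, and exempt the post-infusion draw from the before-dosing requirement;
- state that PK and ADA are covered, and that after a delay the later PK, ADA, Luminex and CyTOF draws follow the actual dose they are tied to;
- say whether the rule applies to the planned surgical gap in staged Cohort B4 patients. Section 6.1.1.2 names only administrative and toxicity delays, while footnote 18 covers any delay.

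In Section 9.5.1, summarise PK by actual time since last dose, using the dose and sample times already recorded.

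The cost is wording in two sections and two footnotes. No samples are added and treatment does not change. The small downside is that, if the draw at the delayed dose also moves, it falls 7 + d days after the previous dose; the actual-time PK analysis handles this.
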